[name] has an ongoing grant (3 R01 MD010629-04S2 – From here after referred to as COVID-19 NJ Study)) which aims to optimize an adaptive intervention to increase testing, and access to treatment and to prevention of COVID-19 infections in a medically or socially vulnerable sample of 670 people in Essex County, NJ. The COVID-19 NJ Study is under the North Jersey Community Research Initiative (NJCRI) IRB oversight, entitled *Optimization of a new adaptive intervention to increase COVID-19 testing among people at high risk in an urban community*, Protocol #: CWCVIDSUPP-UIUC-NJCRI 102497-18274-267805 and has a reliance agreement in place with UIUC.

The new project, COVID-19 IL Study, which is being reviewed by the UIUC IRB, proposes to expand the NJ project to include a sample of 548 people in Illinois. We will use the same protocol that was used in NJ in addition to de-identified data that is currently being collected by the COVID-19 NJ Study. The final study sample will include 670 people from NJ and 548 people from IL for a total of 1,218. Data from the 670 people in NJ will be treated as secondary data and data from the 548 people in IL will be treated as primary data under the COVID-19 IL Study IRB protocol.

The COVID-19 IL Study will use Multiphase Optimization Strategy (MOST) and Community-Based Participatory Research (CBPR) principles and best practices to help facilitate recruitment and to make results readily available to the population. Illinois participants will be randomized two separate times: First, into two distinct groups to receive: (1) navigation services or (2) informational brochure. We aim to help participants to get a COVID-19 test between baseline and the first follow-up (7 days post baseline). Second, after completing the first follow-up, participants are then randomized again to continue with the original intervention or switch to a new one. We then collect data at 2; 5; 12; and 24 weeks post-baseline follow-ups.

The COVID-19 IL Study specific aims include:

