Brochure: This intervention includes two different electronic brochures: One with information about COVID-19 testing (including where and how to get tested), and one with information about COVID-19 prevention and treatment. The brochures will be updated in real time to reflect the most recent CDC public health recommendations. Brochures will be e-mailed to all participants automatically by Redcap upon randomization and one week after they complete the baseline.

Once randomized, all participants will receive the brochure that includes information about testing at CBHC. Navigators will speak to their clients about testing, and, if the participant is interested, they can schedule the COVID-19 test for participants. Note participants will not be pressured to test. They will simply receive the information on how to do so and we will ask them to do it prior to completing their follow-up, if they choose to get tested. Home tests will not be accepted for the purposes of the study.

One week post-baseline, participants will complete the first follow-up survey. Those who received a COVID-19 test between baseline and Follow-up 1 will be randomized to either continue to receive their original intervention (NS or Brochure) or to switch to receive Brief Counseling. Those who fail to get a COVID-19 test between baseline and first follow-up will be randomized to continue the original intervention (NS or Brochure) or switch to receive Critical Dialogue:

Brief Counseling (BC): Brief Counseling is a 15-minute post-COVID-19 test session delivered by a trained licensed clinician in person or via Zoom Conferencing. In the session, the clinician shares the test results and offers recommendations and information about COVID-19 treatment and prevention. Clinicians will be members of the research team and employed by CBHC.

Critical Dialogue (CD): Critical Dialogue includes one two-hour “focus group” session facilitated in person or online by a trained licensed facilitator. Group critical dialogue is prompted by thematic images developed by the Newark Community Collaborative Board (NCCB) to foster a deeper understanding of how systematic stigma, feelings of rage as victims of discrimination, and/or apathy may impact participants’ beliefs and behaviors related to COVID-19 and empower participants to make critical choices to protect their health and the health of their communities.

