COVID-19 Treatment Cascade Optimization Study

NCT05305443

Statistical Analysis Plan

3/30/2022

Statistical Analysis Plan

Data analysis: Aim 1. We will estimate the (1) differences in the effects of first-stage interventions (NS vs brochure), (2) differences in the effects of second-stage interventions (BC vs NS among those who complete testing and referral vs CD among testing decliners), and (3) differences in the effects of selected adaptive interventions on acceptance of testing and adherence to IL recommendations. For differences between NS and brochure, cross-tabulations of the interventions with each outcome will be generated, and crude odds ratios comparing the two will be calculated. For the effects of second-stage and third-stage interventions, we will perform a similar analysis as that for the first-stage interventions but on corresponding subsets as indicated in the specific comparison groups. The estimation of effects of embedded adaptive interventions will use weighted and replicated estimation techniques. Under these procedures, the data set will be restructured wherein an individual's outcome will be replicated in the data set depending on the number of adaptive interventions consistent with this outcome. Since randomization at both stages is based on equal probabilities, weighing is not necessary. The restructuring of the data set as described allows the utilization of standard statistical software for parameter estimation and hypothesis testing. A generalized linear model using logistic regression will be performed where estimation of model parameters will be done using generalized estimating equations due to the presence of replicated subjects. We will then use tests of contrasts to compare selected adaptive interventions. The analysis of the adaptive interventions will be done using PROC GENMOD in SAS. To adjust for baseline characteristics and test for their moderating effects, we will incorporate these terms and their interactions with first-stage, second-stage, and adaptive interventions in their respective models. Only the baseline characteristics will be used for adjustment, as outcomes of the first-stage intervention are biased if incorporated into this model. Odds ratios, 95% CI, and Wald's test for the effect of interventions and covariates will be obtained from these results. Sex/gender and race/ ethnicity will be among these covariates that we will consider for adjustment and moderation analysis.

Interim analyses

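### The SAP's baseline-only adjustment rule, as placed, also covers the second-stage comparisons, where its reason does not apply; the cost is precision and moderator information for adherence outcomes, not bias

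*SAP*

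**What the plan says.** **SAP, Data analysis: Aim 1.** Three sets of effects are to be estimated: first-stage, second-stage and embedded adaptive interventions. The first-stage analysis starts from cross-tabulations and crude odds ratios. For later stages, "we will perform a similar analysis as that for the first-stage interventions but on corresponding subsets as indicated in the specific comparison groups". Covariate models come on top. For baseline characteristics, "we will incorporate these terms and their interactions with first-stage, second-stage, and adaptive interventions in their respective models". The next sentence sets the limit: "Only the baseline characteristics will be used for adjustment, as outcomes of the first-stage intervention are biased if incorporated into this model".

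**Protocol 6A.** On timing, "after completing the first follow-up, participants are then randomized again to continue with the original intervention or switch to a new one".

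**Protocol 7F.** The order is the same: "One week post-baseline, participants will complete the first follow-up survey". Then, "Those who received a COVID-19 test between baseline and Follow-up 1 will be randomized to either continue to receive their original intervention" or to switch to Brief Counseling (BC). Those not tested by then are randomised to continue or to switch to Critical Dialogue (CD).

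**Elsewhere in the SAP.** The Aim 2 logistic models use the first-stage intervention and other covariates, with no limit to baseline. The missing-data section uses first-stage results, together with baseline variables, to impute second-stage results.

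**The concern.** A trial with two randomisations has two baselines. The enrolment survey is the baseline for Navigation Services (NS) against Brochure. Follow-up 1 comes after that assignment but before the second one, so for BC against continuing, and for CD against continuing, it is a pre-randomisation measurement.

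The SAP's one reason for excluding such values is that they are outcomes of the first stage. That is a good reason when the first-stage assignment is part of what is being estimated. It is not a reason when the contrast is between arms of the second randomisation.

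The second-stage comparisons are made on subsets of the sample, so precision matters more there than in the first-stage comparison. A recent pre-randomisation measurement of the same behaviour is often a strong predictor of its later value. As written, an analyst following the SAP would leave it out, both as an adjuster and as a possible moderator of the BC or CD effect.

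**Working it through.** The documents give no power, effect size, testing rate, dropout or correlation, so there is no plan figure to reproduce. The check is a reading of the text, followed by illustrations on assumed inputs.

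**1. Reach of the rule.** The sentence before it names first-stage, second-stage and adaptive-intervention models together. The rule follows with no exception, but refers to a single model. The natural reading includes the second-stage models; a narrower one is possible.

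**2. Order of events.** Protocol 6A and 7F agree: enrolment survey, first randomisation, Follow-up 1, second randomisation. Follow-up 1 is therefore post-randomisation for stage 1 and pre-randomisation for stage 2.

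**3. Does the stated reason hold in each model?** A two-stage trial was simulated with N = 1,218 (670 + 548), 1:1 at both stages, a continuous outcome and 3,000 replicates. Everything except N and the allocation ratio is assumed.

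| Contrast | True effect | Enrolment baseline only | Plus Follow-up 1 |
|---|---|---|---|
| First stage | 0.40 | 0.401 | 0.026 |
| Second stage, testers in one first-stage arm | 0.30 | 0.296 (SD 0.0988) | 0.300 (SD 0.0773) |

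In the first-stage model, adding Follow-up 1 nearly removes the effect, so the SAP is right there. In the second-stage model both versions are essentially unbiased. The variance ratio is (0.0773/0.0988)² = 0.61, about 39% lower with Follow-up 1 in this example.

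**4. How much precision?** Let *e* and *f* be the correlations of the enrolment and Follow-up 1 values with the later adherence score, and *r* their correlation with each other. Then

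R² = (e² + f² − 2efr)/(1 − r²), and residual variance ratio = (1 − R²)/(1 − e²).

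- Follow-up 1 adds little (e = 0.5, f = 0.55, r = 0.8): R² = (0.25 + 0.3025 − 0.44)/0.36 = 0.3125. Ratio = 0.6875/0.75 = 0.917, a fall of about 8%.
- Follow-up 1 carries all that enrolment does, so R² = f²:
  - 0.4/0.6: 0.64/0.84 = 0.76, a fall of 24%.
  - 0.5/0.7: 0.51/0.75 = 0.68, a fall of 32%.
  - 0.6/0.8: 0.36/0.64 = 0.5625, a fall of 44%.

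**5. Rough meaning for power.** Assume half of each first-stage arm is tested by Follow-up 1, with no dropout. Each second-stage arm within one first-stage arm then has 1,218/2 × 0.5/2 ≈ 152 people (68 if only the 548 Illinois participants are used). Take 50% against 65% at two-sided 0.05, by the normal approximation with pooled null variance, and divide n by the variance ratio.

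| Arm size | Reference | 8% fall | 44% fall |
|---|---|---|---|
| 152 | 75.6% | 79.2% (n = 165.8) | 94.4% (n = 270.2) |
| 68 | 42.4% | 45.5% (n = 74.2) | 65.7% (n = 120.9) |

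Scaling n this way suits a continuous score and is only a guide for a binary one. A logistic simulation with the weak-gain correlations (stratum of 600, latent shift 0.25, binary covariates) moved power from about 73% to 75%.

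**The case against.** **Nothing is biased.** This stands. Baseline-only adjustment is valid for a properly randomised second-stage contrast, so a reader who inferred that the second-stage estimates would be wrong would be going beyond the documents.

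**The rule may not reach these models.** The singular wording sits in a paragraph largely about the embedded-strategy model, where the reason is correct. That doubt is real. It does not remove the need for a clarifying edit, because the preceding sentence names the second-stage models.

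**The rule does not cover the whole SAP.** One might read it as barring Follow-up 1 from every analysis. It does not: the Aim 2 models and the imputation models are not so limited, the crude odds ratios use no covariates, and testing by Follow-up 1 is used to form the strata.

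**Testing gains nothing.** Correct. Among testers everyone has tested by Follow-up 1, and among non-testers nobody has. The value is constant within a stratum and cannot be fitted, so the point concerns adherence outcomes only.

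**The gain may be small.** Follow-up 1 comes one week after enrolment, while outcomes run to 24 weeks. The two surveys may be nearly interchangeable as predictors, which is the 8% case. The documents cannot settle this.

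**The comparison groups need defining first.** This also stands. The SAP words the testers' contrast as BC against NS, whereas in Protocol 7F testers from either first-stage arm may continue or switch. Pooling BC recipients from both arms against NS continuers alone is not a purely randomised contrast: in the same simulation the baseline-only estimate was 0.149 against a true 0.30. Follow-up 1 is a clean baseline within testing stratum when first-stage arm is held fixed or modelled.

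**Conclusion.** The point holds in a limited form. A rule that is right for the first-stage and embedded adaptive-intervention models is, as placed, extended to second-stage comparisons where its reason fails. The consequence is lost precision and lost moderator information for adherence outcomes in the adjusted second-stage models; validity is not affected.

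The size is unknown. A further fall in residual variance of roughly 8% to 44% is an illustration that rests wholly on assumed correlations.

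It also rests on the Follow-up 1 survey containing the adherence items. Protocol 7B lists the follow-up surveys under one title and 7F describes tracking adherence over time, which makes this plausible, but the instrument is not reproduced. This is a worthwhile improvement at almost no cost, not a flaw that threatens the trial's conclusions.

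**What to change.** Limit the baseline-only sentence to the first-stage and embedded adaptive-intervention models. Then add wording such as:

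> *In the second-stage comparisons within each testing stratum (testers; non-testers), models for adherence outcomes will also adjust for the Follow-up 1 value of that adherence outcome, measured before the second randomisation, in addition to baseline characteristics, and will include or be stratified by first-stage arm. Follow-up 1 testing status is not a covariate because it defines the strata.*

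Before doing so, confirm that the Follow-up 1 survey carries the adherence items, and state which groups each second-stage contrast compares. If Follow-up 1 variables are wanted as moderators of the second-stage effects, name them in advance.

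The cost is a few SAP sentences, with no new data and no change to the visits. Making the change before the data are analysed avoids a post hoc choice of covariates.

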COVID-19 test procedures and HIPPA protected data collection and sharing: Enrolled participants interested in getting tested for COVID-19 will either come into CBHC or meet the trained outreach worker to collect the sample. CBHC holds a Clinical Laboratory Improvement Amendment (CLIA) Certificate of Waiver and uses the Lumira Dx SARS-CoV-2 Ag Test (see attached instruction manual). The outreach worker will be using N-95 mask and gloves. Participants are asked to collect their own nasal sample and hand it over to the outreach worker who processes it. It takes 15 minutes to obtain the test results and participants are informed immediately. They receive the study brochure that provides

information about how to prevent COVID-19 and what to do if tested positive. As soon as the results come out, the outreach worker logs into Redcap and records the test completion date and results.

In cases where the sample is collected outside of CBHC, the participant will be asked to collect the sample following the instructions, place it into a plastic bag, and hand it to the outreach worker. The collection bag will have the participants' study code number written on it and it is transported in a cooler container back to CBHC. Once the sample is processed, the outreach worker calls the participant to provide the test results and logs the information in Redcap. They receive the brochure when they turn in the sample.

With participants' permission, we will share the COVID-19 test results and some identifying information (e.g., zip codes) with the Duke Clinical Research Institute (DCRI). HIPPA data will be downloaded from Redcap automatically including only data that was authorized by participants to be shared with the CDCC. This will be a CVS file which is downloaded into Box Health. The file is then uploaded weekly into the Duke data portal (see attached CDCC Data guidance pdf).

Participants who report not getting tested in follow-up 3 will be invited to participate in a Critical Dialogue session before completing Follow-up 4.

[figure not shown]

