agree that their institutions may rely on the IRB of UIUC as the designated IRB for review and continuing oversight of its human subjects research described for this project.

[name], [name], [name], and [name] will be available by phone at all times in case an emergency occurs. Any adverse event will be reported to the IRB and funding agency within 24 hours. Through our ICCB collaboration, we have excellent relationships with the community, including community members and agencies that we can mobilize in case the need arises (e.g., access to detox and emergency services, legal support clinics).

Finally, the research team and the clinical team will engage in weekly project meetings to receive ongoing training, discuss the progress of the study and identify and address any potential issues.

13C. Indicate the risk level.

No more than minimal risk

(The probability and magnitude of harm or discomfort anticipated for participation in the proposed research are not greater in and of themselves than those ordinarily encountered in daily life or during the performance of routine physical or psychological examinations or tests).

More than minimal risk (answer 13D)

13D. If you checked that the research is more than minimal risk, describe the provisions for monitoring the data to ensure the safety of subjects, such as who will monitor data and how often, what criteria will be used to stop the research, etc.

The MPIs will oversee data management, including data storage, security, random assignment and quality assurance procedures, REDCap, software and hardware, and will ensure that all staff adheres to Human Subjects guidelines. Data management activities and procedures, including data confidentiality, will employ an electronic data management system to enhance efficiency, security and integrity of study data. The ICCB will also be updated during meetings on data management and adherence to IRB protocol.

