Additionally, integrity assessments will be conducted, which include: (1) a checklist completed by facilitators at the end of each intervention session to list the activities discussed in each session and participant attendance; (2) exit interview. The NCCB and ICCB will review preliminary findings presented by the MPIs on a bi-monthly basis to address any potential adverse reactions that may occur and any safety concerns that may arise. If any participants are found to be unresponsive to the intervention during the course of the study, the Board will discuss the case and the participant may be terminated from the study and referred to relevant services in the community. The MPIs will meet bi-weekly with study staff to review study protocol adherence and address any potential problems. MPI [name] will have weekly supervision meetings with intervention facilitators to review results from fidelity ratings and address any potential deviance from intervention protocols.

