An interim analysis will be conducted bi-monthly by study analysts once data collection starts. This will include the development of syntax to clean the data (e.g., missingness analysis, identification of data entry errors, recoding variables). The key variables will be reviewed. Descriptive data will be presented to PIs and members of the NCCB. The NCCB will review preliminary findings presented by the PIs on a bi-monthly basis to address any potential adverse reactions that may occur and any safety concerns that may arise. If any participants are found to be unresponsive to the intervention, or getting worse during the course of the study, an NCCB sub-committee will discuss the case and the participant may be terminated from the study and referred to relevant services in the community. The PIs will meet weekly with the study staff to review the study protocol adherence and address any potential problems. The PIs will also have weekly supervision meetings with intervention facilitators to review the results from fidelity ratings and address any potential deviance from interventions.

Methods for additional analyses (e.g., subgroup analyses)

Aim 2: To identify other predictors of these outcomes, we will include these variables as covariates using logistic regression analysis. We will model probabilities of testing behavior (completed vs testing decliners) and adherence to IL recommendations as functions of the first-stage intervention and other covariates in the logistic regression analysis.

Qualitative component analysis: Critical dialog sessions and in-depth interviews will be digitally audio-recorded and transcribed. Data will be entered into Atlas ti, a qualitative data processing program. Analysis rooted in phenomenology and grounded theory will include continuous coding, comparison, and recoding to yield categories and connect experiences and themes. The analysis will focus on participant reports about their experiences with the intervention, barriers to testing and adherence to IL recommendations, and suggestions on how to address these barriers.

Methods in analysis to handle protocol non-adherence and any statistical methods to handle missing data

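### The rule allowing participants judged unresponsive to be terminated from the study does not say their follow-up continues, so it permits avoidable, outcome-related loss of later outcomes

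*SAP*

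**What the plan says.** **The rule.** SAP, Interim analyses: "If any participants are found to be unresponsive to the intervention, or getting worse during the course of the study", then "an NCCB sub-committee will discuss the case and the participant may be terminated from the study and referred to relevant services in the community". Protocol 13D: "If any participants are found to be unresponsive to the intervention during the course of the study, the Board will discuss the case", with the same consequence. In 13D lack of response is the only trigger; the SAP adds worsening.

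**Its setting.** In the SAP the preceding sentence is about adverse reactions and safety concerns. Item 13D asks the investigator to "describe the provisions for monitoring the data to ensure the safety of subjects".

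**What the design does with non-testers.** Protocol 7F: "Those who fail to get a COVID-19 test between baseline and first follow-up will be randomized to continue the original intervention" or to switch to Critical Dialogue. Later, "Participants who report not getting tested in follow-up 3 will be invited to participate in a Critical Dialogue session before completing Follow-up 4". 7F also asks all participants for the last two follow-ups, without mentioning anyone already terminated.

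**Analysis.** The SAP's section on non-adherence and missing data plans intent-to-treat grouping and time-ordered multiple imputation. It also plans an examination of missingness by intervention group, adherence, reason for discontinuation, outcome and time.

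**The concern.** Ending an intervention and ending study participation are different acts. Only the second threatens the analysis, and it is the one the rule names. The trigger has no outcome, threshold or time point attached, and the decision is left to a case discussion. If follow-up stops at termination, outcomes after that point are missing for a reason that may be related to the outcome itself.

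A SMART is particularly exposed to this. Non-response at the first stage is the variable on which the second randomisation is tailored, and the later follow-ups measure what happens next. If lack of response were taken to include not testing, the rule would permit removal of people whom the later stages exist to study. Protocol 6A makes outcomes out to 24 weeks part of a primary aim.

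**Working it through.** **1. Is there a figure in the plan to reproduce?** No. Neither document gives a termination rate, outcome rate, dropout rate, effect size or power. The only relevant figures are sample sizes: 548 (Illinois) + 670 (New Jersey) = 1,218. Everything below is therefore illustration under stated assumptions.

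**2. A yardstick.** Illinois only, equal first-stage allocation: 548/2 = 274 per arm. At an assumed 50% outcome rate, the standard error of a difference in proportions is sqrt(2 × 0.25/274) = 4.27 percentage points.

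**3. The most the loss could do.** Let t1 and t0 be the shares terminated in the two arms, r1 and r0 the rates among those retained, and m1 and m0 the unseen rates among those terminated. Then

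true difference = (1 − t1)·r1 + t1·m1 − (1 − t0)·r0 − t0·m0.

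Since m1 and m0 can each lie anywhere from 0 to 1, the range is t1 + t0 wide. With t1 = t0 = t, r1 = r0, and imputation returning r1 − r0, the error is t·(m1 − m0), so at most t.

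| t (assumed) | People per 274 | Largest error | In standard errors |
|---|---|---|---|
| 1% | 2.7 | 1 point | 1/4.27 = 0.23 |
| 2% | 5.5 | 2 points | 2/4.27 = 0.47 |
| 5% | 13.7 | 5 points | 5/4.27 = 1.17 |

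These are outer limits. They require every terminated person in one arm to have the outcome and none in the other.

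**4. What imputation would leave.** A simulation of 2,000,000 people per arm with no true arm effect. Testing at weeks 1, 5 and 12 is about 36% each, linked by a personal propensity that is normal with SD 1 on the logit scale. The week-12 result is lost on termination and imputed within arm from the week-1 and week-5 results. The rates are percentages of the whole arm terminated.

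| Termination falls among | 5% vs 5% | 5% vs 1% | 5% vs 0% | 10% vs 5% |
|---|---|---|---|---|
| Those recorded as untested at weeks 1 and 5 | 0.0 | 0.0 | 0.0 | 0.0 |
| The lowest 40% of the unrecorded propensity | 0.0 | 0.6 | 0.7 | 0.8 |

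Entries are bias in the arm difference, in percentage points. Bias appears only when termination depends on something unrecorded and is used unequally across arms. It then flatters the arm with more terminations. The range of 0.6 to 0.8 points is 0.6/4.27 = 0.14 to 0.8/4.27 = 0.19 standard errors. If 5% and 1% are taken as shares of the low-propensity 40% rather than of the arm (2% vs 0.4% of the arm), the bias falls to 0.2 points.

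The zero for equal use applies to the difference between arms. Each arm's own rate would still be overstated, by about 0.7 points at 5%, as the 5% vs 0% column shows.

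**The case against.** The strongest reply is that this is a rare welfare clause. It sits in safety text, the SAP pairs the trigger with worsening, and the consequence is referral to services. The design also argues against using it on non-testers: they are re-randomised, invited to Critical Dialogue and sampled for interviews, and 7F says nobody will be pressured to test. This reading is plausible. It does not settle the matter, because lack of response to a brochure or a navigator is not a harm, 13D names no other trigger, and even welfare cases are given no stated follow-up.

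The second reply is that the analysis plan already mitigates the loss. That largely stands. Intent-to-treat covers grouping, imputation removes the bias when termination follows recorded data, and missingness will be tabulated by arm and reason for discontinuation. What remains is that a discretionary discussion need not follow recorded data, and the observed data cannot confirm that it did.

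The third reply is that silence in the visible text is weak evidence. The protocol refers to consent forms (14G) and a safety monitoring plan (16D) that are not available here, and the 7F statement about the last follow-ups excludes nobody. This is a fair limit. But the rule as written says participants are terminated from the study, so an exception held elsewhere should be stated beside it.

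Two stronger inferences should be resisted. A reader might note that the NCCB helped develop Critical Dialogue and infer that its sub-committee would favour that arm; nothing shows unequal use, and the visible text does not say whether the sub-committee knows the arm. A reader might also count bi-monthly reviews falling within follow-up as exposure; a meeting is an opportunity, not a termination.

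**Conclusion.** The point holds as a wording defect with a small, conditional risk. Both documents state a rule that permits outcome-related loss of later outcomes, and that loss is avoidable. The size and direction of any bias cannot be derived, and it may be zero. It stayed below 1 point in the imputation scenarios tried, which rest on assumed testing rates, an assumed propensity and termination rates that no document supports.

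A reader might infer that the trial's odds ratios will be materially distorted. Suppose testing is 40% in both arms and 20% of would-be non-testers are terminated in one arm only. A complete-case analysis would then see 0.40/(0.40 + 0.60 × 0.80) = 45.5% in that arm, an odds ratio of (0.455/0.545)/(0.40/0.60) = 1.25. That does not describe this plan: the SAP specifies multiple imputation, and nothing suggests one-sided termination on that scale. The documents therefore support a recommendation to change the rule, but not a finding of bias.

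**What to change.** For Illinois, change the rule in both SAP Interim analyses and Protocol 13D:

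1. Remove lack of response as a ground for ending study participation.
2. Allow the intervention to be stopped, with referral, for safety or welfare reasons.
3. State that scheduled surveys and REDCap test records continue unless consent is withdrawn, and that the outcomes so observed enter the intent-to-treat analysis.

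Suggested text: *If a safety or welfare concern arises, the intervention may be stopped and the participant referred to services. Scheduled surveys and test records continue unless consent is withdrawn, and these outcomes are analysed as randomised.*

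The safety and referral power is kept. The cost is wording in two places and a few more surveys that are already scheduled. Test capture is already in place, since 7F says that "the outreach worker logs into Redcap and records the test completion date and results". Tabulation by arm and reason needs no new provision, because the SAP's missingness review largely covers it. New Jersey data are collected under another IRB's oversight, so there it is enough to report whether such a rule was used.
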